6.3.2 Dose modification and dose interruption for spartalizumab and siltuximab

General dose modification instructions:

Siltuximab and spartalizumab have class-specific safety profiles based on their mechanism of action but may also cause AEs that overlap. For management of AEs which can be clearly attributed to siltuximab or spartalizumab, independent dose modification for either agent is allowed. For AEs without clear attribution to either study treatment, management of toxicity should include dose modifications of both agents.

Overall AEs are to be graded according to NCI-CTCAE v4.03 (http://ctep.cancer.gov). All dose interruptions and the reason for the dose interruption must be documented in the eCRF.

Overall, patients with AEs suspected to be related to *spartalizumab* including those of potential immune-mediated etiology (irAE) may need to interrupt or permanently discontinue spartalizumab as outlined in Section 6.3.2. In general, study treatment with spartalizumab must be permanently discontinued in case of:

- Any life-threatening adverse reactions (excluding endocrinopathies controlled with hormone replacement therapy)
- Persistent Grade 2 or 3 adverse reactions (excluding endocrinopathies controlled with hormone replacement therapy) that do not recover to <= Grade 1 within 12 weeks after last dose of study treatment
- Inability to reduce the dose of steroids (for the management of irAE) to 10 mg/day or less of prednisone or equivalent (or as indicated in the tables below) within 12 weeks
- Any severe or Grade 3 recurring treatment-related adverse reaction

The 12 weeks' timeframe will begin from the time the irAE reaches a grade that leads to spartalizumab interruption.

Overall, patients with AEs suspected to be related to *siltuximab* include pruritus, increased weight (edema), rash, hyperuricemia, neutropenia, and upper respiratory tract infection. Rare side effects include gastrointestinal perforation. Toxicities may require interruption of therapy,

Protocol/Version No.: 5, Date December 15, 2022

dose reduction or permanent discontinuation from trial as detailed in section 6.3 and Tables 8-8 and 8-9. In general study treatment with siltuximab must be discontinued for:

- Gastrointestinal perforation
- Grade 4 weight gain
- Grade 4 upper respiratory tract infection
- Recurrent or severe grade 3 treatment-related adverse events.
- Life threatening adverse events
- Interruption of therapy for longer than 12 weeks

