If either study drug (siltuximab or spartalizumab) is on temporary hold, therapy with the other agent will continue. Cross sectional imaging will be performed every 3rd cycle as per protocol. If there is disease progression, the subject should be removed from the study. The only exception is siltuximab may be continued as a single agent to control immune-related adverse events (irAEs) attributed to spartalizumab, but siltuximab therapy must be stopped after the irAEs can be adequately controlled with corticosteroids therapy.

If either study drug (siltuximab or spartalizumab) is being **permanently** discontinued, the remaining study drug should also be permanently discontinued given that either drug alone is unlikely to have adequate anti-tumor activity to justify its continuation for a prolonged period of time with the following exceptions:

- 1. In subjects who are demonstrating objective benefit from treatment (radiologic CR, PR or SD), a discussion regarding continuing single agent therapy will be conducted with PI and patient. Subject will be informed single agent activity of either agent is unlikely in pancreatic cancer. If the subject is agreeable, single agent therapy may continue until progression. No single agent therapy beyond progression will be offered.
- 2. Siltuximab may be continued as a single agent to control immune-related adverse events (irAEs) attributed to spartalizumab, but siltuximab therapy must be stopped after the irAEs can be adequately controlled with corticosteroids therapy.

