other clinical sequelae (e.g., renal impairment, pulmonary infiltrates) Grade 4: Life-threatening; pressor or ventilatory support indicated	 Acetaminophen Narcotics Oxygen Pressors Corticosteroids Epinephrine Increase monitoring of vital signs as medically indicated until the patient is deemed medically stable in the opinion of the investigator. Hospitalization may be indicated. 	

2nd occurrence of grade 2 irAE (including colitis/diarrhea, LFT abnormalities, rash, nephritis and other AEs as listed in table 8-6) or for grade 2 irAE lasting more than 12 weeks. Permanently discontinue spartalizumab.

6.3.2.1.2 Guidance for corticosteroids tapering for management of immune-related AEs:

Steroids should be tapered slowly and based on response/recovery of clinical symptoms. Consider to complete tapering over a period of at least 4 weeks. Slower tapering of corticosteroids therapy may be recommended if the adverse event is not showing improvement.

Protocol/Version No.: 5, Date December 15, 2022

Once corticosteroid tapering is achieved at a level of 10 mg of prednisone/day (or equivalent), spartalizumab can be restarted as indicated in the dose modification tables.

6.3.2.2 Dose modification requirements for adverse events suspected to be related to study treatment

The required dose modification and management of adverse events that are considered to be related to study medication and do not have specific management requirements noted elsewhere in the protocol are provided in Table 8-8 & Table 8-9.

Table 8-8 Mandatory dose modification requirements and recommended clinical management guidelines for hematologic adverse events suspected to study treatment

Hematologic su	spected AEs (NCI-CTCAE v4.03)	
Grade	Recommended Adverse Event management guidelines	Mandatory Dose Modification requirements
Neutropenia		
Grades 1, 2	NA	Continue spartalizumab and siltuximab

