6.4.2 Prohibited Concomitant Medications

During the course of the study, patients must not receive other antineoplastic therapies (e.g. investigational drugs, devices, chemotherapy, immunotherapies) or any other therapies that may be active against cancer or modulate the immune responses. However, limited-field palliative radiotherapy may be allowed as concomitant therapy (see above).

The use of systemic steroid therapy and other immunosuppressive drugs is not allowed except for the treatment of infusion reaction, irAEs, and for prophylaxis against imaging contrast dye allergy, standard pre-medication for chemotherapy or replacement-dose steroids in the setting of adrenal insufficiency (providing this is < 10 mg/day prednisone or equivalent), or transient exacerbations of other underlying diseases such as COPD requiring treatment. If systemic corticosteroids are required for the control of infusion reactions or irAEs, it must be tapered and be at non-immunosuppressive doses (< 10 mg/day of prednisone or equivalent) before the next administration of study treatment. If the dose of prednisone or equivalent cannot be reduced to less than 10 mg/day before the administration of next dose of study treatment then spartalizumab or siltuximab must be discontinued (note: next dose can be delayed up to 12 weeks).

The use of live vaccines is not allowed through the whole duration of the study. Inactivated vaccines are allowed.

There are no prohibited therapies during the post-treatment follow-up period except for live vaccines within 4 weeks of last administration of siltuximab.

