6.6.3 Study treatment packaging and labeling

Study treatment, spartalizumab, will be provided as global clinical open supply and will be packed and labeled under the responsibility of Novartis, Drug Supply Management.

Study treatment, Siltuximab, will be provided by EUSA Pharmac (UK) Ltd.

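### During a temporary spartalizumab hold for a steroid-treated immune event, Section 6.3.2 continues siltuximab while Section 6.4.2, read literally, bars it until steroids are below 10 mg/day

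*Combined protocol and SAP*

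**What the plan says.** **Section 6.3.2.** If an adverse event can be clearly attributed to one drug, "independent dose modification for either agent is allowed". If it cannot, "management of toxicity should include dose modifications of both agents". When either drug is on temporary hold, "therapy with the other agent will continue". The same section adds that "siltuximab may be continued as a single agent to control immune-related adverse events (irAEs) attributed to spartalizumab", but that siltuximab must stop once corticosteroids control the event. That provision appears twice: in the temporary-hold paragraph, after a sentence on removal at progression, and again as an exception to the rule that permanent discontinuation of one drug ends both.

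**Tables 8.0 to 8-6.** These interrupt or stop spartalizumab only. They recommend systemic steroids for many of the same events.

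**Section 6.3.2.1.2.** On taper length: "Consider to complete tapering over a period of at least 4 weeks". Once the taper reaches 10 mg/day, spartalizumab may restart. Siltuximab is not mentioned.

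**Section 6.4.2.** Where systemic steroids are needed for an infusion reaction or immune-related event, "it must be tapered and be at non-immunosuppressive doses (< 10 mg/day of prednisone or equivalent) before the next administration of study treatment". If that is not achieved, "then spartalizumab or siltuximab must be discontinued (note: next dose can be delayed up to 12 weeks").

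**The concern.** An investigator with a patient on prednisone for a spartalizumab-attributed event has to decide whether to give the next siltuximab infusion. Section 6.3.2 says yes and Section 6.4.2 says not yet. Neither refers to the other, and no rule of precedence is given.

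Two things are at stake. The first is conduct: the plan does not settle whether patients receive an IL-6 antibody while on high-dose steroids, in a combination that Section 5.2 describes as new. The second is interpretation: two investigators following the same protocol could produce different siltuximab exposure after the same event, so the toxicity profile at the RP2D could mix two managements.

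Exposure may also affect who is analysed. Section 12.3 makes patients who take less than 80% of their prescribed siltuximab and spartalizumab inevaluable for toxicity. If that means both drugs must fall short, and if withheld doses count as prescribed, then missing 2 of 8 siltuximab infusions (6/8 = 75%) could decide the matter for a patient already short on spartalizumab. The SAP states neither condition, so this is a possible consequence and not a demonstrated one.

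**Working it through.** There is no planned figure to reproduce. The check compares the passages and then asks how often the conflict would arise.

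**1. Does the term used in 6.4.2 include siltuximab?** Yes. Section 6.6.3 reads "Study treatment, Siltuximab, will be provided by EUSA". The siltuximab stopping list in 6.3.2 uses the same term for siltuximab. The consequence sentence in 6.4.2 itself names siltuximab.

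**2. Which events fall under both rules?** Three conditions are needed: clear attribution to spartalizumab, a temporary hold, and systemic steroids at 10 mg/day or more. Examples from the tables:
- First Grade 3 diarrhea/colitis (Table 8.0): prednisone 1-2 mg/kg after intravenous steroid.
- First Grade 3 rash (Table 8-2): 1 mg/kg.
- Grade 2 nephritis (Table 8-3): 0.5-1 mg/kg, rising to 1-2 mg/kg if not improving. First Grade 3 nephritis: 1-2 mg/kg.
- First Grade 2 pneumonitis (Table 8-4): 1-2 mg/kg if clinically indicated.
- First Grade 3 event in the other category (Table 8-6): 1-2 mg/kg.

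**3. Which events fall outside?**
- Unclear attribution: both drugs are modified.
- Permanent spartalizumab discontinuation, for example Grade 4 events, Grade 3-4 liver events, Grade 3-4 pneumonitis and encephalitis: the temporary-hold rule does not apply and siltuximab generally stops too. The two exceptions in 6.3.2 can still reach some of these patients.
- Grade 2 liver events: spartalizumab is held, but Table 8-1 recommends no steroids.
- Endocrinopathy that is not life-threatening: Table 8-5 lets steroids be omitted.

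**4. Does an infusion fall due in the disputed period?** Inputs: 21-day cycles (Section 6.2), a ±3-day window (6.3.4), a taper of T = 28 days (6.3.2.1.2, recommended only) and the 10 mg/day threshold (6.4.2). Assumptions: 70 kg and a linear taper to zero from starting dose D. The dose at day t is D(1 − t/T), which falls below 10 mg/day when t > T(1 − 10/D).
- 0.5 mg/kg, D = 35: 28 × (25/35) = 20.0 days
- 1 mg/kg, D = 70: 28 × (60/70) = 24.0 days
- 2 mg/kg, D = 140: 28 × (130/140) = 26.0 days

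Body weight is not given, so the range from 50 to 90 kg is:
- 0.5 mg/kg: 28 × (15/25) = 16.8 to 28 × (35/45) = 21.8 days
- 1 mg/kg: 28 × (40/50) = 22.4 to 28 × (80/90) = 24.9 days
- 2 mg/kg: 28 × (90/100) = 25.2 to 28 × (170/180) = 26.4 days

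Time at full dose before the taper lengthens each of these. From 1 mg/kg upward the period exceeds 21 days, so a nominal Day 1 falls inside it, although the ±3-day window can move the actual infusion. At 0.5 mg/kg the period is about one cycle, and an infusion can miss it.

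**5. The longer colitis taper.** Table 8.0 gives 45 to 60 days, but only after infliximab for Grade 3 events that do not improve in 2-3 days. From 70 mg/day: 45 × (60/70) = 38.6 days, or 38.6/21 = 1.8 cycles; 60 × (60/70) = 51.4 days, or 51.4/21 = 2.4 cycles.

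**The case against.** The strongest reply is that the sections can be harmonised. Section 6.3.2 lists failure to reduce steroids as a reason to stop spartalizumab only; the siltuximab list has no such item. Section 6.3.2.1.2 ties restart to spartalizumab only. Section 6.4.2 says one drug or the other must stop, not both. The exception in 6.3.2 plainly expects siltuximab to be given before steroids have controlled the event. On this reading the 10 mg/day condition governs only the held drug.

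That reading is plausible, and it is why the finding is that the text supports two instructions, with neither clearly prevailing. It does not remove the conflict. The operative sentence in 6.4.2 covers all study treatment without limit, exempts nothing and refers to nothing in 6.3.2. Read literally, it also largely cancels the exception, because siltuximab is allowed there mainly while steroids are not yet sufficient, when doses would ordinarily be above 10 mg/day.

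A reader might infer that giving siltuximab during high-dose steroids has been shown to be unsafe. The documents do not show this. The Castleman's disease trial in Section 4.1.2.1 adjusted for corticosteroid use at randomization, and Section 6.5.1.2 allows corticosteroids to be considered around a restarted siltuximab infusion. No doses are given in either place, so these passages do not establish safety either. The point rests on the contradiction and not on evidence of harm.

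**Conclusion.** The contradiction stands in the current text for steroid-treated events clearly attributed to spartalizumab that lead to a temporary hold, mainly first-occurrence Grade 2-3 events. In those patients a scheduled siltuximab infusion will usually, but not always, fall while steroids are at or above 10 mg/day. The timing rests on the assumed body weight, the linear shape and a taper length that is only recommended.

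Three stronger readings are tempting and not supported:
- That every steroid-treated immune event is affected. Unclear attribution, permanent discontinuation and events managed without steroids fall outside the temporary-hold conflict.
- That every course blocks at least one infusion, and colitis at least two. That counts the whole course instead of the time at or above 10 mg/day. A 0.5 mg/kg start can block none, and a 45-day taper from 70 mg/day guarantees only one.
- That different sites would diverge. Oversight, sample storage and drug disposal all sit at one cancer centre; divergence between investigators is enough for the point.

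No sample size, error rate or escalation rule is shown to change. The point matters because two instructions conflict on whether an investigational infusion is given.

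**What to change.** Reconcile three places: Section 6.3.2 (the temporary-hold rule and the provision for siltuximab to control immune events), Section 6.3.2.1.2 (restart after taper) and Section 6.4.2. State once whether the 6.4.2 steroid condition governs spartalizumab, siltuximab or both, say which section prevails, and carry the rule into Tables 8.0 to 8-6 so that each table says what happens to siltuximab. The same edit can align the threshold, which is 10 mg/day or less in 6.3.2, a level of 10 mg/day in 6.3.2.1.2 and below 10 mg/day in 6.4.2. Which rule to adopt is the sponsor's clinical decision.

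The cost is amendment wording. Optionally, add a derived flag for siltuximab infusions given during systemic steroids, built from the dosing and concomitant-medication records already collected. A separate adverse event summary for those infusions is not required.

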6.3.2.1 Dose Modification requirements for potential immune- mediated adverse events

6.3.2.1.1 Identification of and management requirements for AEs of potential immune-mediated etiology (irAE)

Adverse events of special interest (AESI) include AEs of a potential immune-mediated etiology (irAE) that are associated with spartalizumab treatment. An irAE may be experienced by patients treated with spartalizumab due to its mechanism of action and predicted based on the reported experience with other immunotherapies that have a similar mechanism of action.

Protocol/Version No.: 5, Date December 15, 2022

Investigators must be vigilant and carefully identify AEs that may be suggestive of potential irAEs as their appearance may be sub-clinical and early diagnosis is critical for its adequate management and resolution.

An irAE may be of low grade and self-limited, most frequently involving the GI tract (i.e. diarrhea/colitis), skin (i.e. rashes), liver (i.e. hepatitis), lung (i.e. pneumonitis), kidneys (i.e. nephritis) and endocrine systems (a variety of endocrinopathies) and rarely CNS (i.e. encephalitis), however, nearly all organs can be affected by immune-mediated toxicities. irAEs often occur relatively early (mostly within weeks to 3 months after treatment initiation), however, may develop at any time during treatment (even after several months), and may also occur after the treatment discontinuation. Serological, immunological and histological assessments should be performed as deemed appropriate by the investigator, to verify the potential immune-related nature of the AE, and exclude a neoplastic, infectious or metabolic origin of the AE.

Severe grade or persistent lower grade irAEs typically require interrupting or permanently discontinuing treatment and administration of systemic steroids, and sometimes other immunosuppressive medications (i.e. tumor necrosis factor alpha (TNFa) antagonists, mycophenolate or tacrolimus, etc.). Early recognition and work-up of irAEs and initiation of treatment are critical to reduce the risk of complications, since the majority of irAEs are reversible with the use of steroids and other immune suppressants. Some events like endocrinopathies may require life-long hormonal replacement. Tapering of steroids should not be too rapid to avoid recurrence or worsening of irAEs. The management of irAEs may further include initiation of antibiotics for prophylaxis against opportunistic infections.

Patients should be instructed to return to the study site as soon as possible (instead of waiting for their next scheduled visit) if they experience symptoms consistent with an irAE. Patients who experience a new or worsening irAE should be contacted and/or evaluated by the study site more frequently.

Based on experience from compounds with similar mechanism of action of spartalizumab and published guidelines (Haanen, 2017), instructions have been developed regarding how to identify, assess severity and manage irAEs that may occur in patients receiving spartalizumab. Dose modification requirements and AE management guidelines for the potential irAEs are provided in the following tables: diarrhea/colitis (Table 8-0), hepatitis (liver laboratory alterations) (Table 8-1), skin (rash) (Table 8-2), nephritis (Table 8-3), pneumonitis (Table 8-4), endocrinopathies (Table 8-5), and other potential immune-related AEs (Table 8-6). Any Grade 4 irAE must result in permanent discontinuation of spartalizumab. In addition, guidance for management of spartalizumab -infusion reaction & cytokine release syndrome is provided in (Table 8-7).

Under the category of OTHERS (Table 8-9) are included several irAE of interest that must be managed specifically and for which no specific guidance are provided in the table below. OTHERS include (but is not restricted to) the following events: Autoimmune neuropathy, demyelinating polyneuropathy, Guillain-Barre, myasthenia Gravis-like syndrome, non-infectious myocarditis, non-infectious pericarditis, pancreatitis, encephalitis, and, rapid onset of Grade 3 fatigue in the absence of disease progression.

Protocol/Version No.: 5, Date December 15, 2022

Patients receiving spartalizumab, may experience other irAEs than those listed in this document, therefore, all AEs of unknown etiology associated with drug exposure should be evaluated to determine if it is possibly immune-related. In cases where the specific irAE is not listed in the tables below, the investigator should follow the dose modification requirements in section 6.3.2 which details the measures to be taken for suspected (could be potentially immune-related or non-immune-related) AEs. Investigators are encouraged to contact the Sponsor as needed to discuss cases that warrant separate discussion outside of the scope of the current instructions.

The dosing modification requirements are mandatory, however, the AE management guidelines are recommendations and can be modified according to the local practices.

Table 8.0 Mandatory dose modification requirements and recommended clinical management guidelines for potential immune-related diarrhea/colitis

Diarrhea/Colitis (NCI-CTCAE v	1100/	
Grade	Recommended Adverse Event management guidelines	Mandatory Dose Modification requirements
Grade 1 (< 4 bowel actions per day over baseline) mild Grade 2 (4-6 bowel actions per day over baseline) and / or abdominal pain/ blood in stool.	 Diet Hydration Loperamide: initially 4 mg, followed by 2 mg every four hours or after every unformed stool; maximum 16 mg/day. Continue until diarrhea free for 12 hours; Diarrhea > 24h: loperamide 2 mg every two hours; maximum 16 mg/day. Consider adding oral antibiotics. Diarrhea > 48hrs: loperamide 2 mg every two hours; maximum 16 mg/day. Consider other second-line therapies for diarrhea (e.g: (octreotide, oral diphenoxylate) and oral antibiotics If Grade 2 and no improvement in 5 days may require oral steroids If Grade 2 diarrhea persists >1 week consider Gl consultation and endoscopy to 	Continue spartalizumab treatment If diarrhea is Grade 2, despite loperamide at 2 mg every two hours for > 48hrs:

Protocol/Version No.: 5, Date December 15, 2022

Diarrhea/Colitis (NCI-CTCAE v4.03) Grade **Recommended Adverse Mandatory Dose Modification Event management** requirements guidelines • If Grade 2 persists for 5 days and worsening of symptoms or diffuse ulcerations and bleeding seen on endoscopy, commence steroids at a dose of 0.5-1mg/kg per day of prednisone (or IV equivalent) and continue until symptoms improve to Grade 1. If no improvement occurs, manage as per Grade 3. Steroids can be tapered as per section 6.3.1.2.2. Sigmoidoscopy and biopsy can be considered and may assist in determining the duration of steroid taper based on the evidence of macroscopic and microscopic inflammation. Grade 3 Diarrhea: Increase of Clinical evaluation and 1st occurrence: ≥7 stools per day over baseline; hospitalization indicated: Interrupt spartalizumab until incontinence; hospitalization rule out bowel perforation diarrhea/colitis recovers to indicated; limiting self-care ADL; and intravenous hydration. Grade ≤1 or baseline Consider consultation with Once recovered restart gastroenterologist and Grade 3 Colitis: Severe spartalizumab treatment confirmation biopsy with abdominal pain; change in at the same dose and bowel habits: medical endoscopy. schedule and after intervention indicated: appropriate steroid In addition to symptomatic peritoneal signs tapering (if initiated). treatment (diet, hydration, loperamide, antibiotics if indicated); initiate AE resolution to ≤ Grade 1 or immediate treatment with baseline must occur within a intravenous steroids period of 12 weeks since a (methylprednisolone 125 Grade 3 event has been mg) followed by high dose identified, otherwise oral steroids (prednisone 1 spartalizumab must be to 2 mg/kg once per day or permanently discontinued dexamethasone 4 mg every 4 hours) is recommended. 2nd occurrence: When symptoms improve to Permanently discontinue ≤Grade 1, steroid taper spartalizumab should be done as per section 6.3.1.1.2.

Taper over 6 to 8 weeks in patients with diffuse and

Diarrhea/Colitis (NCI-CTCAE v4.03)		
Grade	Recommended Adverse Event management guidelines	Mandatory Dose Modification requirements
	severe ulceration and/or bleeding.	
	 If no improvement in 2-3 days: consider initiating infliximab 5mg/kg and continue steroids. (Infliximab is contraindicated in patients with sepsis or a perforation). Upon symptomatic relief initiate a prolonged steroid taper over 45 to 60 days. 	
	 If symptoms worsen during steroid reduction, initiate a re-tapering of steroids starting at a higher dose of 80 or 100 mg followed by a more prolonged taper and administer infliximab. If symptoms persist despite the above treatment a surgical consult should be 	
	obtained.	
Grade 4: Life-threatening consequences; urgent intervention indicated	Same as Grade 3	Permanently discontinue spartalizumab

Table 8-1 Mandatory dose modification requirements and recommended clinical management guidelines for potential immune-related liver laboratory alterations

Abnormal liver function tests		
Severity	Recommended Adverse Event management guidelines	Mandatory Dose Modification requirements
Grade 2: AST or ALT > 3x ULN to ≤ 5.0x ULN and/or bilirubin > 1.5x ULN to ≤ 3x ULN (if patient meets criteria for Hy's law refer to section	Monitor hepatic laboratory tests more frequently (every 2-3 days) until returned to baseline values	 Interrupt spartalizumab treatment until recovery to Grade ≤1 or baseline Once recovered restart spartalizumab treatment at the same dose and schedule
6.5)		 Patients with baseline grade 2 AST/ALT value (>3.0-5.0 ULN) may continue spartalizumab treatment

Protocol Study No: Winship4463-18 Product: Siltuximab plus Spartalizumab Protocol/Version No.: 5, Date December 15, 2022

Abnormal liver function tests		
Severity	Recommended Adverse Event management guidelines	Mandatory Dose Modification requirements
Grade 3 or 4: AST or ALT >5.0xULN and/or bilirubin > 3.0x ULN	 Monitor hepatic laboratory tests more frequently (every 2-3 days) until returned to baseline values. Consider viral serology (i.e. hepatitis A/B/C, CMV, and rule out other potential cause of liver injury such as conmeds or alcohol), consultation with hepatologist and liver biopsy to establish etiology of hepatic injury If after 2-3 days new liver assessment shows worsening of laboratory test consider to initiate treatment with steroids prednisone 1-2 mg/kg/day or IV equivalents. Add prophylactic antibiotics for opportunistic infections as appropriate When symptoms/liver function tests improve to Grade ≤1, taper steroids over at least 4 weeks. If serum transaminase levels or bilirubin do not decrease 48 hours after initiation of systemic steroids, oral mycophenolate mofetil 500 mg every 12 hours may be given as per local treatment guidance. Infliximab is not recommended due to its potential for hepatotoxicity 	 Permanently discontinue spartalizumab Patients with baseline grade 2 AST/ALT value (>3.0-5.0 ULN) will discontinue spartalizumab treatment if value increased to grade 3 with increase >=2x baseline

Table 8-2 Mandatory dose modification requirements and recommended clinical management guidelines for potential immune-related skin events

Rash Events (NCI-CTCAE v4.03)		
Grade	Recommended Adverse Event management guidelines	Mandatory Dose Modification requirements
Grade 1: Rash covering < 10% Body Surface Area (BSA)	 Initiate prophylactic and symptomatic treatment measures. Consider use of topical corticosteroids or urea containing creams in combination with oral antipruritics or moderate strength topical steroid (hydrocortisone 2.5% cream or fluticasone propionate 0.5% cream) 	Continue spartalizumab treatment
Grade 2: 10-30% of BSA	 Reassess after 2 weeks. If tolerable, treat as per Grade 1; If intolerable, initiate systemic steroids (e.g. oral prednisolone 0.5-1mg/kg daily) and consider dose interruption until tolerable or recovery to grade <=1 or baseline; once recovered resume spartalizumab treatment at the same dose and schedule. If symptoms persist or recur consider skin biopsy. 	Continue spartalizumab treatment AE resolution to ≤1 or baseline must occur within a period of 12 weeks since Grade 2 event has been identified, otherwise spartalizumab must be permanently discontinued.
Grade 3: More than 30% of BSA	 Obtain a skin biopsy and dermatology consult. Initiate systemic steroids with 1mg/kg of prednisolone or IV equivalent. 	 1st occurrence: Interrupt spartalizumab until rash recovers to Grade ≤1 or baseline Once recovered restart spartalizumab treatment at the same dose and schedule AE resolution to ≤ Grade 1 or baseline must occur within a period of 12 weeks since Grade 3 event has been identified.

Rash Events (NCI-CTCAE v4.03)		
Grade	Recommended Adverse Event management guidelines	Mandatory Dose Modification requirements
		Otherwise, spartalizumab must be permanently discontinued
		2 nd occurrence:
		Permanently discontinue spartalizumab
Grade 4: Life-threatening	Same as Grade 3; additional measures as per local institutional guidelines	Permanently discontinue spartalizumab
Other skin events		
Stevens-Johnson syndrome, toxic epidermal necrolysis and other serious or life-threatening skin reactions	Institute supportive care immediately as per institutional guidelines	Permanently discontinue spartalizumab

Table 8-3 Mandatory dose modification requirements and recommended clinical management guidelines for potential immune-related nephritis

Nephritis (NCI-CTCAE v4.03)		
Grade	Recommended Adverse Event management guidelines	Mandatory Dose Modification requirements
Grade 1: Creatinine >ULN to ≤1.5x ULN)	 Monitor creatinine weekly If creatinine return to baseline resume routine creatinine monitoring per protocol Promote hydration and 	Continue spartalizumab
	cessation of nephrotoxic drugs	
Grade 2: Creatinine >1.5 to ≤3 x ULN	 Monitor creatinine every 2 to 3 days Initiate 0.5 to 1 mg/kg/day prednisone or equivalents If worsening or no improvement: 1 to 2 mg/kg/day prednisone or 	 Interrupt spartalizumab until serum creatinine recovers to ≤ Grade 1 or baseline. Once recovered restart spartalizumab at the same dose and schedule
	 equivalents Promote hydration and cessation of nephrotoxic drugs Consult with specialist and consider renal biopsy 	AE resolution to ≤ Grade 1 must occur within a period of 12 weeks since Grade 2 event has been identified, otherwise spartalizumab must be permanently discontinued.

Nephritis (NCI-CTCAE v4.03)		
Grade	Recommended Adverse Event management guidelines	Mandatory Dose Modification requirements
Grade 3: Creatinine >3.0 to <6 x ULN	 Monitor creatinine every 1 to 2 days Start 1 to 2 mg/kg/day prednisone or equivalents Consult with nephrologist and consider renal biopsy 	1st occurrence: • Interrupt spartalizumab until serum creatinine recovers to ≤Grade 1 or baseline. • Once recovered restart spartalizumab treatment at the same dose and schedule AE resolution to ≤ Grade 1 or baseline must occur within a period of 12 weeks since the Grade 3 event has been identified, otherwise spartalizumab must be
Grade 4: Creatinine >6x ULN	 Monitor creatinine daily Initiate steroids with 1 to 2 mg/kg/day prednisone or equivalent Consult with nephrologist and consider renal biopsy 	permanently discontinued 2 nd occurrence: Permanently discontinue spartalizumab. Permanently discontinue spartalizumab

Table 8-4 Mandatory dose modification requirements and recommended clinical management guidelines for potential immune-related pneumonitis

Pneumonitis (NCI-CTCAE v4.03)		
Grade	Recommended Adverse Event management guidelines	Mandatory Dose Modification requirements
Grade 1: Radiographic changes only- Asymptomatic	 CT scan (high-resolution with lung windows) recommended, with serial imaging to monitor for resolution or progression-re-image at least every 3 weeks Monitor for symptoms every 2-3 days - Clinical 	

Protocol Study No: Winship4463-18 Product: Siltuximab plus Spartalizumab Protocol/Version No.: 5, Date December 15, 2022

Grade	Recommended Adverse Event management guidelines	Mandatory Dose Modification requirements
	evaluation and laboratory work-up for infection	
	 Monitoring of oxygenation via pulse oximetry recommended 	
	 Consultation of pulmonologist recommended 	
Grade 2: Symptomatic-medical	CT scan (high-resolution	1 st occurrence:
intervention indicated; limits instrumental ADLs	with lung windows)	Interrupt spartalizumab until receivers to Crede <1
motiumental ABES	 Monitor symptoms daily, consider hospitalization 	until recovery to Grade ≤1 or baseline
	Clinical evaluation and laboratory work up for infection	 Once recovered restart spartalizumab treatment at the same dose and
	Consult pulmonologist	schedule
	 Pulmonary function tests - if normal at baseline, repeat every 8 weeks 	AE resolution to ≤ Grade 1 or baseline must occur within a
	Bronchoscopy with biopsy and/or BAL recommended	period of 12 weeks since Grade 2 event has been
	 Symptomatic therapy including corticosteroids if clinically indicated (1 to 2 	identified, otherwise spartalizumab must be permanently discontinued.
	mg/kg/day prednisone or equivalent as clinically indicated).	If worsens treat as Grade 3 or 4
		2 nd occurrence:
		Permanently discontinue spartalizumab
Grade 3: Severe symptoms; limits self-care ADLs; oxygen	 CT scan (high-resolution with lung windows) 	Permanently discontinue spartalizumab
Grade 4: Life threatening	 Clinical evaluation and laboratory work-up for infection 	
Grade 4: Life- threatening respiratory compromise; urgent intervention required	Consult pulmonologist	
	 Pulmonary function tests-if < normal, repeat every 8 weeks until ≥ normal 	
	Bronchoscopy with biopsy and/or BAL if possible	
	Treat with IV steroids (methylprednisolone 125 mg) as indicated. When	

Pneumonitis (NCI-CTCAE v4.03)		
Grade	Recommended Adverse Event management guidelines	Mandatory Dose Modification requirements
	symptoms improve to ≤ Grade 1, a high dose oral steroid (prednisone 1 to 2 mg/kg once per day or dexamethasone 4 mg every 4 hours). If IV steroids followed by high dose oral steroids does not reduce initial symptoms within 48 to 72 hours, consider non- corticosteroid immunosuppressive medication	

Table 8-5 Mandatory dose modification requirements and recommended clinical management guidelines for potential immune-related endocrine events

Grade	Recommended Adverse Event management guidelines	Mandatory Dose Modification requirements
Asymptomatic, intervention not indicated (e.g. hyperthyroidism or hypothyroidism)	 If TSH <0.5x LLN, or TSH >2x ULN, or consistently out of range in 2 subsequent measurements, include free T4 at subsequent cycles as clinically indicated Consider endocrinologist consult If hypophysitis is considered, pituitary gland imaging should be considered (MRIs with gadolinium and selective cuts of the pituitary can show enlargement or heterogeneity and confirm the diagnosis) Repeat labs in 1 to 3 weeks/MRI in 1 month if laboratory abnormalities persist but normal lab/pituitary scan 	Continue spartalizumab

Protocol/Version No.: 5, Date December 15, 2022

Grade	Recommended Adverse Event management guidelines	Mandatory Dose Modification requirements
Symptomatic endocrinopathy (e.g., hypophysitis, adrenal insufficiency, hypothyroidism, hyperthyroidism)	 Consider Endocrinology consultation Rule out infection/sepsis and other alternative causes with appropriate cultures and imaging Treat with an initial dose of methylprednisolone 1 to 2 mg/kg intravenously followed by oral prednisone 1 to 2 mg/kg per day. (only for lifethreatening endocrinopathies) Replacement of appropriate hormones may be required as the steroid dose is tapered Hypophysitis with clinically significant adrenal insufficiency and hypotension, dehydration, and electrolyte abnormalities (such as hyponatremia and hyperkalemia) constitutes adrenal crisis Consider hospitalization and intravenous methylprednisolone should be initiated. 	Interrupt spartalizumab until recovery to mild or no symptoms, and controlled with hormone replacement therapy Once recovered or controlled with hormone replacement, restart spartalizumab at the same dose and schedule Hypothyroidism may be managed with replacement therapy without treatment interruption (unless lifethreatening) Permanently discontinue spartalizumab for lifethreatening endocrinopathies (i.e. hyperthyroidism, adrenal insufficiency, hypophysitis) or recurring severe/lifethreatening events not controlled by hormone replacement therapy.
Autoimmune diabetes (Grade 3 or symptomatic hyperglycemia)	Initiated: Initiate anti-glycemic therapy (i.e. insulin) as medically indicated and monitor glucose levels regularly until metabolic control is achieved	Interrupt spartalizumab until recovery to grade 1 or baseline Once recovered, restart spartalizumab treatment at the same dose and schedule
Autoimmune diabetes (Grade 4 hyperglycemia or life- threatening complications)	Same as Grade 3	 Second occurrence: permanently discontinue Permanently discontinue spartalizumab

Management for immune-related:

Protocol/Version No.: 5, Date December 15, 2022

a. For non-life-threatening immune-related endocrinopathy, the administration of corticosteroids can be omitted, and the patient can be treated with physiologic replacement of the deficient hormone (e.g. provide levothyroxine for immune-related hypothyroidism, and omit administration of corticosteroids).

b. Use corticosteroids only used if endocrinopathy is life-threatening or as physiologic replacement for primary or secondary adrenal insufficiency.

